9.4.2. Primary Objective

The primary analysis for the primary objective will be conducted once the last participant has completed the Week 72 visit and database lock has achieved.

The primary efficacy endpoint is achieving a sustained virologic response for 24 weeks after the planned end of GSK3228836 and PegIFN sequential treatment in the absence of rescue medication. Sustained virologic response is defined as observing HBsAg <LLOQ and HBV DNA <LLOQ at each analysis window in the 24 weeks after the end of sequential treatment. Analysis windows for the post sequential treatment assessments will be defined in the analysis plan.

HBsAg and HBV DNA from the week of end-of-treatment to Off-Treatment Week 24 will be used to assess the primary endpoint for each arm.

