4.2. Primary Endpoint Analyses

HBsAg and HBV DNA assessments from the end of treatment analysis window (Week 48 or Week 36 for Arm 1 and Arm 2 respectively) to the off-treatment Week 24 analysis window will be used to analyse the primary endpoint for each arm. The primary analysis for the primary endpoint will be conducted once the database lock has been achieved and the last participant has completed the Week 72 visit.

The primary efficacy endpoint is achieving a sustained virologic response for 24 weeks after the planned end of GSK3228836 and PegIFN sequential treatment in the absence of rescue medication. Sustained virologic response (SVR) is defined as observing HBsAg <LLOQ and HBV DNA <LLOQ at each analysis window in the 24 weeks after the end of sequential treatment. Analysis windows for the post GSK3228836 treatment assessments are defined in Section 4.2.2.1.

An estimation approach with no hypothesis testing will be used to address the primary objective. The primary assessments of interest are the point estimate of SVR rate and 95% credible intervals. In addition, posterior probabilities that the true SVR rate in each treatment arm is greater than a range of clinically meaningful response rates will be provided. The point estimates for SVR will be calculated using a Bayesian probability approach. Comparisons between treatment arms as defined in the key secondary/exploratory objectives will be assessed using probability inference approaches.

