Analysis Set	Parameter	Target Study Day	Analysis Window		Analysis Timepoint	Protocol Visit
			Beginning Timepoint	Ending Timepoint		
Efficacy	HBsAg and HBV DNA	78	64	Minimum of (98, PegIFN First Dosing Study day)	End of GSK3228836 treatment	Week 12
Efficacy	HBsAg and HBV DNA	246	211	266	End of PegIFN Treatment / EoT	Week 36
Efficacy	HBsAg and HBV DNA	302	267	322	Post PegIFN treatment Week 8	Off-treatment Week 8
Efficacy	HBsAg and HBV DNA	372	323	378	Post PegIFN treatment Week 18	Off-treatment Week 18
Efficacy	HBsAg and HBV DNA	414	379	434	Post PegIFN treatment Week 24	Off-treatment Week 24

The primary analysis will be based on planned end of treatment regardless of whether a patient discontinued treatment.

For the first and second supplementary estimands described in Section 4.2.4.1 and Section 4.2.4.2, SVR will be measured from actual rather than planned end of treatment and the analysis windows should be amended accordingly. For these estimands, the date of last dose should be treated as the reference date and the rules in Table 4 should be used to determine the endpoint of SVR.

Table 4 Supplementary Endpoint Analysis Visit Windows for Arm 1 and Arm 2

Analysis Set / Domain	Parameter	Reference Day	Analysis Window		Analysis Timepoint
			Beginning Timepoint	Ending Timepoint	
Efficacy	HBsAg and HBV DNA	Reference date	Reference date - 35	Reference date + 20	End of Actual treatment
Efficacy	HBsAg and HBV DNA	Reference date + 56	Reference date + 21	Reference date + 76	Post treatment Week 8
Efficacy	HBsAg and HBV DNA	Reference date + 126	Reference date + 77	Reference date + 132	Post treatment Week 18
Efficacy	HBsAg and HBV DNA	Reference date + 168	Reference date + 133	Reference date + 188	Post treatment Week 24

If all analysis windows have non-missing response information, a participant's response (Responder or Non-responder) is determined as follows:

1. If rescue medication was used during on-treatment or off-treatment period, then the participant is a non-responder.
2. If HBsAg <LLOQ and HBV DNA <LLOQ in each of the analysis windows, then the participant is a responder, otherwise the participant is non-responder.
3. A result of TND is considered as <LLOQ.

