If all HBsAg and HBV DNA data within the analysis window for the EOT visit is missing due to a WDE, and the participant withdraws from the study due to the WDE, the participant will be classified as not reaching EOT at follow-up. Data after the intercurrent event will be set to missing, and their SVR response will be imputed assuming missing at random using all available data from participants for whom SVR can be assessed.

If all HBsAg and HBV DNA data within the analysis window for the EOT visit is missing due to a WDE, but the participant later returns to study and has non-missing data in an analysis window, the data will be handled in the following two ways:

1. For observed VR responders, the data will be analysed as collected (treatment policy). No imputation of missing data will be performed.
2. For observed VR non-responders, data collected after the intercurrent event will be set to missing. Their SVR response will be imputed assuming missing at random using all available data from participants for whom SVR can be assessed (hypothetical strategy).

If all HBsAg and HBV DNA data within an analysis window after the planned end of sequential treatment (EoT) is missing unrelated to wide disruptive events, missing data will be considered as an SVR non-responder. No imputation of missing data will be performed.

If all HBsAg and HBV DNA data within an analysis window after the planned end of sequential treatment (EoT) is missing due to wide disruptive events, the participant's SVR status will be considering as missing due to WDE. Data after the intercurrent event will be set to missing, and the SVR response will be imputed using all available data from participants for whom SVR can be assessed.

If the participant has any HBsAg \geq LLOQ or HBV DNA \geq LLOQ or rescue medication usage at or after the planned end of sequential treatment (EoT), the subject will be classified as an SVR non-responder. No imputation of missing data will be performed.

If a participant has any assessments that are affected by a wide disruptive event, but the participant's HBsAg and HBV DNA within an analysis window are collected and the participant is a VR responder, the subject will be classified as an SVR responder.

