4.7.4.2. Missing Primary Data Post End of Treatment

If all HBsAg and HBV DNA data within an analysis window post the planned end of sequential treatment (EoT) and before/at the assessment is missing not due to wide disruptive events, missing data will be considered as a non-response.

If all HBsAg and HBV DNA data within an analysis window post the planned end of sequential treatment (EoT) and before/at the assessment is missing due to wide disruptive events (such as COVID-19 pandemic) and the participant doesn't have any HBsAg \geq LLOQ or HBV DNA \geq LLOQ or rescue medication at or post planned end of sequential treatment (EoT), the subject will be classified as a potential SVR responder and will be counted among number of participants with VR success at end of treatment (EoT) and maintained until IA (nvr2 in Table 9).

If a participant has any assessments that are affected by a wide disruptive event, but the participant's HBsAg and HBV DNA within an analysis window are collected and the participant is a VR responder, the subject will be classified as a potential SVR responder and will be counted among number of participants with VR success at end of treatment (EoT) and maintained until IA (nvr2 in Table 9).

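### The last wide-disruptive-event rule in SAP 4.2.2.2 gives final SVR-responder status for virologic response within one analysis window, although SVR requires every window

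*SAP*

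**What the plan says.** Protocol 9.4.2 defines sustained virologic response as "HBsAg <LLOQ and HBV DNA <LLOQ at each analysis window in the 24 weeks after the end of sequential treatment". SAP 4.2 repeats this ("defined as observing HBsAg <LLOQ and HBV DNA <LLOQ at each analysis window in the 24 weeks after the end of sequential treatment") and uses "HBsAg and HBV DNA assessments from the end of treatment analysis window" up to off-treatment Week 24. SAP Tables 2 and 3 make that four windows per arm: end of treatment (EoT) and post-treatment Weeks 8, 18 and 24.

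SAP 4.2.2.1 gives the derivation for complete data. Its condition is "If all analysis windows have non-missing response information", and its second step reads "If HBsAg <LLOQ and HBV DNA <LLOQ in each of the analysis windows, then the participant is a responder, otherwise the participant is non-responder".

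SAP 4.2.2.2 then handles disrupted and incomplete data. In summary:

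- EoT or later window missing, unrelated to a WDE: SVR non-responder.
- Later window missing because of a WDE: SVR status missing, then imputed.
- EoT window missing because of a WDE and the participant withdraws: imputed. If the participant returns, observed responders are analysed as collected; observed non-responders have later data set to missing and SVR imputed.
- Any value at or above LLOQ, or rescue use, at or after EoT: SVR non-responder.
- Last rule: if any assessment was affected by a WDE, but the HBsAg and HBV DNA results "within an analysis window are collected and the participant is a VR responder, the subject will be classified as an SVR responder".

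For the interim analysis, SAP 4.7.4.2 has a parallel rule with a different outcome: "the participant is a VR responder, the subject will be classified as a potential SVR responder". Protocol 9.4.2.3 says that SVR is imputed where a WDE prevents its assessment, and that the participant is a non-responder where SVR cannot be ascertained for other reasons.

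**The concern.** The last rule refers to data in one window and to VR, yet it assigns the participant-level final outcome, SVR. The SAP keeps the two apart. Section 4.2.2.2 determines VR at EoT from the EoT window. Section 4.7.1 counts VR at EoT separately from SVR. Section 4.7.3.1 classes participants who have VR at EoT but do not sustain it as SVR failures. So VR responder cannot simply be read as SVR responder.

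This is the derivation of the primary endpoint. If the sentence is programmed as it stands, a participant with an incomplete off-treatment record can be a success under one rule and a failure, or an imputed value, under another. Two programmers could derive different primary results from the same data. SAP Table 10, which lists changes to the protocol-defined analyses, mentions no change to the protocol's missing-data rules.

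**Working it through.** **1. The rules applied to the same participant.** Each participant below has at least one assessment affected by a WDE and is below LLOQ at EoT.

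| Later off-treatment windows | Other rules | Last rule as written |
|---|---|---|
| All below LLOQ | Responder | Responder |
| One missing, unrelated to a WDE | Non-responder (SAP 4.2.2.2; protocol 9.4.2.3) | Responder |
| One missing because of a WDE | Imputed (same sections) | Responder |
| One at or above LLOQ, or rescue used | Non-responder (preceding paragraph of SAP 4.2.2.2) | Responder, if that paragraph is ignored |

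**2. How many data patterns are affected.** Let each of the four windows be below LLOQ, at or above LLOQ, or missing because of a WDE. That gives 3^4 = 81 patterns.

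- At least one window below LLOQ, so the last rule read literally gives SVR: 81 − 2^4 = 65.
- All four below LLOQ, so the definition is met: 1.
- A mix of below LLOQ and WDE-missing only: 2^4 − 2 = 14.
- At least one window below LLOQ and at least one at or above it: 65 − 1 − 14 = 50.

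The 50 are covered by the preceding paragraph on values at or above LLOQ. The 14 are where the last rule does harm. Protocol 9.4.2.3 would impute all 14. Within the SAP, 7 have EoT observed and a later window missing, so the imputation rule applies directly. In another 6, EoT and a later window are both missing, so the imputation rule and the return-to-study rule both bear. In the last 1, only EoT is missing and the return-to-study rule analyses the data as collected. If the missing windows are instead unrelated to a WDE, all 14 are non-responders under the SAP. These are counts of patterns, not of participants.

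**3. Size per participant.** With 50 per arm (SAP section 5), one participant is 1/50 = 2 points.

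- Alternative is non-response: gain = 2 points.
- Alternative is imputation with probability q: gain = 2 × (1 − q). Taking q from the true rates in SAP Table 12, as an assumption: 1.6 points at 20%, 1.4 at 30%, 1.2 at 40%.

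**4. The plan's own figures, then an illustration.** With a Beta(0.5, 0.5) prior, the posterior for r responders of 50 is Beta(r + 0.5, 50 − r + 0.5). The smallest r giving more than 65% posterior probability is 12 for a rate above 20% and 17 for a rate above 30%, as in Table 12. The chance of at least 12 at a true rate of 30% is 86.1% (stated ~86%). The chance of at least 17 at a true rate of 40% is 84.4% (stated 84%).

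Now suppose k of 50 participants are made responders regardless and the other 50 − k respond at the true rate. The documents give no k.

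| k | ≥12 of 50, true rate 20% | ≥17 of 50, true rate 30% |
|---|---|---|
| 0 | 29% | 32% |
| 1 | 39% | 39% |
| 2 | 50% | 48% |
| 3 | 62% | 57% |

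On the same planning model, the posterior probability of a rate above 30% is 0.628 at 16/50 and 0.735 at 17/50.

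**The case against.** The strongest reply is that the sentence complements those before it. They deal with windows in which everything is missing; this one deals with a window in which data were collected despite a disruption. On that view it says only that a WDE does not void collected values below LLOQ, and the definition in SAP 4.2 still requires each window. That is a plausible intention, but the text does not say it: the outcome assigned is final SVR status, and no phrase ties it back to every window.

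Several limits do stand. A reader might infer that a documented relapse would be counted as SVR. The preceding paragraph of SAP 4.2.2.2 makes any value at or above LLOQ, or rescue use, from EoT onward a non-response, so the documents do not support that. A reader might also infer that the interim word *potential* was lost in copying. That is conjecture: nobody's follow-up is pending at the final analysis, and the two sections differ elsewhere. Only the difference in outcome is documented.

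Nor do the documents show a decision being reversed. The 16/50 and 17/50 figures come from the unstratified planning model, whereas the final analysis is a logistic model with strata and pooled arms (SAP 4.2.2). The 65% criterion appears only in the operating characteristics, no formal hypothesis test is planned, and the internal decision framework sits in a separate charter.

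Finally, one might want to rank every observed value at or above LLOQ ahead of WDE imputation. The primary estimand does not allow it. SAP 4.2.1 uses a hypothetical strategy for WDEs that lead to discontinuation, significant interruption or non-adherence. SAP 4.2.2.2 and the footnote in 4.2.2.1 accordingly treat observed non-response affected by a WDE as missing.

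**Conclusion.** The point holds. As written, the last rule of SAP 4.2.2.2 contradicts the every-window definition of the primary endpoint. For participants with another window missing, it also contradicts the non-response and imputation rules. The conflict that matters is confined to those incomplete records.

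The direction is certain, because the rule assigns only success. The gain is up to 2 points per affected participant in an arm of 50 where the alternative is non-response, and about 1.2 to 1.6 points where it is imputation at an assumed 20% to 40%. The total effect is unknown: the documents do not give the number of participants with a WDE-affected assessment, VR in some window and another window missing, and it may be zero. The values k = 1 to 3 are illustrative only.

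A separate inconsistency remains within the same section. One paragraph makes any value at or above LLOQ from EoT onward a non-response; others set observed non-response after a qualifying WDE to missing.

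**What to change.** Replace the outcome in the last rule of SAP 4.2.2.2 with: *the participant is a virologic responder for that analysis window; SVR still requires HBsAg <LLOQ and HBV DNA <LLOQ in the EoT window and every off-treatment window, with missing windows handled by the non-WDE (non-responder) and WDE (imputation) rules above.*

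In the same revision, state when a value at or above LLOQ from EoT onward is non-response and when, after a qualifying WDE, it is set to missing and imputed, in line with the hypothetical strategy of the primary estimand. Say also how a WDE-missing EoT window followed by values below LLOQ is to be handled, since the return-to-study rule and the every-window definition both bear on it.

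The cost is one replaced sentence, a short clarification and a check of the derivation program. It needs no new data and no design change, and the stated operating characteristics are unaffected. Reporting how many participants meet the last rule with a window missing would show whether the ambiguity affected any result.

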4.2.2.3. Model Checking and Diagnostics – MCMC Mixing Diagnosis

Two sampling chains will be run, with differing starting values and each with a burn-in period of 5,000 samples, to ensure adequate sampling from the posterior. The starting values will be as described above in Section 4.2.2.

Mixing will be regarded as “each chain is independently realizing values similar to those for which the other chains have also sampled.” Adequate mixing will be concluded if the chains meet following conditions:

1. The Brooks-Gelman Ratio (BGR) (Brooks, 1998) for each parameter is in the interval (0.8, 1.2).
2. Each chain appears mix well, upon visual inspection of each chain's trace plot, including assessing the mutual overlap of the chains for each parameter.
3. Each kernel density plot appears smooth upon visual inspection.

4.2.3. Sensitivity Analyses

For the primary estimand, a sensitivity analysis will be performed using the Bayesian model described in Section 4.2.2. The final inference from the Bayesian model will account for the missing data assuming MAR, regardless of the reason for missingness.

4.2.4. Supplementary Estimands

The following supplementary estimands are defined to support the primary objective.

4.2.4.1. Measuring SVR from Actual End of Treatment instead of Planned End of Treatment

The first supplementary estimand is defined in the same way as the primary estimand, except the assessment time frame for participants achieving SVR will be 24 weeks after the actual end of treatment. The estimand strategy for handling treatment discontinuation unrelated to wide disruptive events will be while-on-treatment, which calculates the actual duration from the first to the last dose of treatment received. See Section 4.2.1 for additional details.

4.2.4.2. Measuring SVR from Actual End of Treatment by Categorical Subgroups of PegIFN Treatment Duration

The second supplementary estimand supporting the primary objective measures SVR from actual end of treatment by categorical subgroups of PegIFN treatment duration.

The second supplementary estimand is defined as:

- **Population:** Participants with CHB on stable NA therapy that are eligible for PegIFN.
- **Treatment:** 300 mg GSK3228836 for 12 or 24 weeks followed by up to 24 weeks of PegIFN therapy while on stable NA therapy.
- **Variable:** The percentage of participants that achieve SVR for 24 weeks after the actual end of sequential treatment without the use of rescue medication

- **Intercurrent Events:**
 - Significant interruption in or non-adherence to PegIFN related or unrelated to WDEs will be analysed as collected (treatment policy strategy).
 - Discontinuation and delayed start of PegIFN related or unrelated to WDEs will be handled by calculating the actual duration using the first to the last dose of PegIFN received (while-on-treatment strategy).
 - Use of rescue medication will be incorporated in the definition of the endpoint (composite strategy).
- **Population Summary:** The percentage of participants achieving SVR for 24 weeks after the actual end of treatment by PegIFN treatment duration categorical grouping of at least 12, 16, 20, and 24 weeks of PegIFN treatment in each treatment arm.

4.2.4.3. Measuring SVR from Planned End of Treatment for Participants who Received At Least Twelve Doses of PegIFN

The third supplementary estimand examines the effect of the intercurrent event of a participant failing to meet PegIFN eligibility criteria by PegIFN Eligibility Week 13 (i.e. can no longer receive at least 12 weeks of PegIFN treatment). The estimand strategy for this intercurrent event will be principal stratum, which restricts the population to participants for whom the intercurrent event did not occur. The third supplementary estimand is defined as:

- **Population:** Participants with CHB on stable NA therapy that have received at least 12 doses of PegIFN
- **Treatment:** 300 mg GSK3228836 for 12 or 24 weeks followed by up to 24 weeks of PegIFN therapy while on stable NA therapy.
- **Variable:** The percentage of participants that achieve SVR for 24 weeks after the planned end of sequential treatment without the use of rescue medication
- **Intercurrent Events:**
 - For discontinuation of, interruption in, or non-adherence to GSK3228836 or PegIFN unrelated to any wide disruptive events (such as COVID-19 pandemic), the data will be analysed as collected (treatment policy strategy).
 - For participants that are ineligible to receive PegIFN, the data will be analysed as collected (treatment policy strategy).
 - Use of rescue medication will be incorporated in the definition of the endpoint (composite strategy).
 - For wide disruptive events (such as COVID-19 pandemic) leading to discontinuation of, significant interruption in, or non-adherence to GSK3228836 and PegIFN, data collected after the intercurrent event will be set to missing and the response will be imputed assuming missing at random in the Bayesian model (hypothetical strategy).

- **Population Summary:** The percentage of participants in each treatment group who achieve SVR for 24 weeks after the planned end of sequential treatment without use of any rescue medication.

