5.1. Inclusion Criteria

AGE
1. At least 18 to 75 years of age at the time of signing the informed consent [if country/site age requirements for consent differ, the more stringent (e.g., higher age) restriction will be required for that country/site].
TYPE OF PARTICIPANT AND DISEASE CHARACTERISTICS
2. Participants who are eligible to be treated with PegIFN (Table 8)
3. Documented chronic HBV infection ≥ 6 months prior to screening AND currently receiving stable NA therapy except telbivudine, defined as no changes to their NA regimen from at least 6 months prior to screening and with no planned changes to the stable regimen over the duration of the study
4. Plasma or serum HBsAg concentration > 100 IU/mL
5. Plasma or serum HBV DNA < 90 IU/mL
6. Alanine Transaminase (ALT) ≤ 2 X ULN

SEX
7. Male and/or Female 
 a. A male participant is eligible to participate if they agree to the following during the intervention period and for at least 90 days after the last dose of study treatment 
 i. Refrain from donating sperm ii. AND be abstinent from heterosexual intercourse as their preferred and usual lifestyle (abstinent on a long term and persistent basis) and agree to remain abstinent OR Must agree to use contraception/barrier as detailed below 
 1. Agree to use a male condom [and should also be advised of the benefit for a female partner to use a highly effective method of contraception as a condom may break or leak] when having sexual intercourse with a woman of childbearing potential who is not currently pregnant b. A female participant is eligible to participate:

- i. If she is not pregnant or breastfeeding
 - ii. AND at least one of the following conditions applies:
 1. Is not a woman of childbearing potential (WOCBP) as defined in Section 10.4 Contraception and Barrier Guidance
 2. Is a WOCBP and using a contraceptive method that is highly effective (with a failure rate of <1% per year), preferably with low user dependency during the intervention period and for at least 90 days after the last dose of study treatment
- A WOCBP must have a negative highly sensitive pregnancy test (urine or serum as required by local regulations) within 24 hours before the first dose of study intervention, see Section 10.2.

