- Population Summary: The percentage of participants achieving SVR for 24 weeks after the actual end of treatment by PegIFN treatment duration categorical grouping (groupings to be defined in the RAP) in each treatment arm.

The second supplementary Estimand (supporting the primary objective in participants with CHB on stable NA therapy) is percentage of participants achieving SVR for 24 weeks after the actual end of treatment by PegIFN treatment duration categorical grouping in each treatment arm, taking into account discontinuation and delayed start of PegIFN, regardless of interruption in and other non-adherence to PegIFN, regardless of discontinuation of, interruption in and non-adherence to GSK3228836. The PegIFN treatment duration will support interpretation of the percentage of participants achieving SVR for 24 weeks after the actual end of treatment, especially if participants discontinue from PegIFN early or delay start of PegIFN due to ineligibility.

The third supplementary Estimand is defined in the same way as the main Estimand, except the strategy for intercurrent events of PegIFN ineligibility for more than 12 weeks (i.e. can no longer receive at least 12 weeks of PegIFN treatment) and/or missing at least 12 doses

of PegIFN will be principal stratum. This supplementary Estimand supporting the primary objective is the percentage of participants in each treatment arm that achieve SVR (HBsAg <LLOQ and HBV DNA <LLOQ) for 24 weeks after the planned end of sequential treatment in participants with CHB on stable NA therapy and receiving at least 12 doses of PegIFN, in the absence of rescue medication, regardless of discontinuation of, interruptions in or non-adherence to GSK3228836 had they not been affected by wide disruptive events.

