	
The main primary estimand supporting the primary objective in participants with CHB on stable NA therapy in each treatment arm is the percentage of participants that achieve SVR (HBsAg <LLOQ and HBV DNA <LLOQ) for 24 weeks after the planned end of sequential treatment in the absence of rescue medication, regardless of ineligibility to receive PegIFN, discontinuation of, interruption in, and non-adherence to GSK3228836 and PegIFN, had they not been affected by wide disruptive events.
 
Three supplementary Estimands are defined to support the primary objective:
 
 • The first supplementary Estimand is defined in the same way as the main Estimand, except the assessment time frame for patients achieving SVR will be 24 weeks after the actual end of treatment. Therefore, the strategy for intercurrent events of treatment discontinuation will be while-on-treatment. This supplementary estimand supporting the primary objective in participants with CHB on stable NA therapy in each treatment arm is the percentage of participants that achieve SVR (HBsAg <LLOQ and HBV DNA <LLOQ) for 24 weeks after the actual end of sequential treatment in the absence of rescue medication, regardless of ineligibility to receive PegIFN, discontinuation of, interruption in, and non-adherence to GSK3228836 and PegIFN, had they not been affected by wide disruptive events. • The second supplementary Estimand is to understand the relationship between the PegIFN duration and achieving SVR for 24 weeks after the actual end of treatment, defined as: 
 ○ Population: Participants with CHB on stable NA therapy ○ Treatment: 300 mg GSK3228836 for 12 or 24 weeks followed by 24 weeks of PegIFN therapy while on stable NA therapy ○ Variable: The relationship between SVR for 24 weeks after actual end of treatment and the duration of PegIFN received by participants ○ Intercurrent Events: 
 ▪ Discontinuation and delayed start of, PegIFN, will be accounted to reflect the actual duration from the first to the last dose of PegIFN received (while-on-treatment strategy).

Objectives	Estimands and Endpoints

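### SAP 4.2.4.2 narrows the PegIFN-duration estimand to PegIFN-eligible participants without declaring it, and its groups have no row for no PegIFN or under 12 weeks

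*SAP*

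**What the plan says.** SAP 1.1 introduces the analysis: "The second supplementary Estimand is to understand the relationship between the PegIFN duration and achieving SVR for 24 weeks after the actual end of treatment". Its population line there is "Population: Participants with CHB on stable NA therapy", with no eligibility condition, and protocol 9.4.2.2 gives the same population.

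SAP 4.2.4.2, the section to be programmed, gives the population as "Participants with CHB on stable NA therapy that are eligible for PegIFN". It reports SVR by "categorical grouping of at least 12, 16, 20, and 24 weeks of PegIFN treatment in each treatment arm" and measures duration by "calculating the actual duration using the first to the last dose of PegIFN received".

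Protocol 9.4.2.2 leaves the cut-points open ("groupings to be defined in the RAP") but not the population. It says duration helps in interpreting SVR "especially if participants discontinue from PegIFN early or delay start of PegIFN due to ineligibility".

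Protocol 4.1 expects some participants never to receive PegIFN, namely those still ineligible at PegIFN Eligibility Week 13. SAP Table 10, the list of changes from the protocol, has no entry narrowing this population. Its one entry on populations points the other way and aligns the efficacy objectives with ITT, meaning all randomised participants.

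**The concern.** There are two separate problems. The first is a contradiction: one estimand has two populations within the SAP, and the narrower one departs from the protocol without being declared. The second is a weakness in a choice that the SAP was entitled to make: the groups start at 12 weeks.

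Together they remove the low-exposure end from an analysis meant to describe how SVR varies with PegIFN exposure. The people removed are unlikely to be a random subset. Protocol 5.3 makes post-GSK3228836 eligibility depend on ALT, blood counts and psychiatric status, and protocol 8.3.7.1 links therapeutic ALT flares to antiviral effect. Their SVR rate could therefore be lower or higher than that of the participants shown.

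**Working it through.** The plan gives no figure for the number of ineligible or short-exposure participants, so there is no stated number to reproduce. The check is mainly a comparison of definitions.

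**1. Population.** Protocol 9.4.2.2 and SAP 1.1 have no eligibility restriction; SAP 4.2.4.2 has one. The restriction carries no time point. Inclusion criterion 2 (protocol 5.1) already requires PegIFN eligibility at entry, and protocol 5.3 reassesses it after GSK3228836.

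**2. Allocation to the SAP groups under each reading of eligibility.**

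| Participant | Eligible at entry | Eligible after GSK3228836 | Row in table |
|---|---|---|---|
| Never started because ineligible | In population | Not in population | None |
| Started, stopped before 12 weeks | In population | In population | None |
| 12 to <16 weeks | In population | In population | At least 12 |
| 20 to <24 weeks | In population | In population | At least 12, 16 and 20 |

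The missing rows do not depend on which reading is meant.

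**3. The duration metric.** SAP 4.2.4.2 counts from first to last dose but gives no formula. I assume the exposure formula of SAP 4.5.1 applies: weeks = (last injection date − first injection date + 1) / 7. For *d* on-schedule weekly doses this is ((*d* − 1) × 7 + 1) / 7. Planned doses come from protocol Table 6 and SAP 6.1.5.

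- 24 doses (eligible at Week 1): (23 × 7 + 1)/7 = 162/7 = 23.14 weeks
- 15 doses (eligible at Week 10): (14 × 7 + 1)/7 = 99/7 = 14.14 weeks
- 12 doses (eligible at Week 13): (11 × 7 + 1)/7 = 78/7 = 11.14 weeks

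On that formula, a Week 13 starter who takes every planned dose also has no row. A full-course participant misses the at-least-24-week group unless the ±3-day windows stretch the span to its maximum, (162 + 6)/7 = 24.0 weeks. Delayed starters with 15 to 23 planned doses (14.14 to 22.14 weeks) do fall in a group.

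**4. Size, by illustration.** Assume 50 per arm (the planned size) and 12 responders, so 12/50 = 24%. Let *m* participants have no row and *k* of them respond. The at-least-12-week rate is (12 − *k*)/(50 − *m*).

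| *m* | *k* = 0 | *k* = 2 |
|---|---|---|
| 3 | 12/47 = 25.5% | 10/47 = 21.3% |
| 5 | 12/45 = 26.7% | 10/45 = 22.2% |
| 10 | 12/40 = 30.0% | 10/40 = 25.0% |
| 15 | 12/35 = 34.3% | 10/35 = 28.6% |

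The values of *m* and *k* are assumptions, and the direction depends on *k*.

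**The case against.** The strongest reply is that the protocol delegated the groupings, so cumulative bands from 12 weeks are a permitted choice. That stands for the cut-points. It does not cover the population, which was not delegated.

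A second reply is that if eligibility means eligibility at entry, nothing was narrowed. On that reading the added words do nothing. Elsewhere the SAP treats PegIFN ineligibility as an intercurrent event, which suggests the later assessment. The wording needs settling either way, and the missing rows remain.

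Three stronger readings are tempting but not supported:

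- *That early discontinuers and delayed starters as a whole disappear.* They do not. Those with 12 or more weeks appear, and protocol 9.4.2.2 does not name never-starters; they come in through its unrestricted population.
- *That nested groups cannot show a duration-response pattern.* Bands above 12 weeks can be derived by subtraction: with assumed counts of 10/40 for at least 12 weeks and 9/30 for at least 24, the band between is 1/10. The participants without a row can be roughly recovered as one pool by comparison with the first supplementary estimand. That is approximate, because wide disruptive events are handled differently there, and it cannot separate never started from stopped early.
- *That never-starters are the only evidence on whether PegIFN adds benefit.* Protocol 2.1 and SAP 4.2.2 address that question by comparison with study 209668, and SAP 4.3.1.1 adds a time-to-relapse analysis from the end of GSK3228836. Never-starters are a selected group and weak evidence on it. Raised ALT need not prevent a PegIFN start either, because eligibility is reassessed up to Week 13.

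Finally, SAP 4.4 is partly redacted and could contain a related display.

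**Conclusion.** The concern holds in two parts. The population in SAP 4.2.4.2 contradicts protocol 9.4.2.2 and SAP 1.1, and the change is undeclared; this is an error as written. The absence of rows below 12 weeks is a permitted choice that serves the stated purpose poorly, because no visible analysis shows SVR at low PegIFN exposure.

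The effect is limited to one descriptive supplementary estimand. The primary estimand keeps these participants under treatment policy, and no hypothesis is tested. The number affected is unknown, so the illustrated rates show what could happen and are not estimates. The 11.14- and 23.14-week spans assume on-schedule dosing and the SAP 4.5.1 formula. Even with all rows shown, the comparison across durations would be confounded by the reasons for short exposure.

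**What to change.** In SAP 4.2.4.2:

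1. Restore the protocol population (all ITT participants). If the restriction is intended, say at which assessment eligibility is judged and declare the change in Table 10.
2. Add a row for never started and a row for more than 0 but under 12.
3. Report non-overlapping groups on one stated metric. Dose count works: 0, 1–11, 12–15, 16–19, 20–23 and 24. It places a Week 13 starter with all 12 planned doses, and a full-course participant with 24, in the rows a reader would expect, which the calendar formula does not.
4. State that for never-starters the reference date in SAP Table 4 is the last GSK3228836 dose. This follows from the last-dose rule in SAP 4.2.2.1 but is not spelled out.

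The cost is SAP wording and one re-cut table. With about 50 per arm some cells will be small, so the table stays descriptive and sparse rows may be pooled.
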